- h. For multiple dose expansion, ASP0598 Otic Solution or placebo administration on Day 15 and Day 29 will be conducted in the case that the TMP closure is not confirmed. If the treatment is not conducted on these visits, imaging pictures and Microscopic ear examination for skin local reaction after the drug administration will be skipped.

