| Visit Windows | Week | | | Week 2 | Week 4 | Week 6 | Week 8 | Week 12 | Week 16 |
| Visit number | | 1 | 2 | 3 | 4 | 5 | 6 | 7 | 8 |
| Study Procedures | | | | | | | | | |
| Informed Consent | | X | | | | | | | |
| Verify Inclusion/Exclusion | | X | X | | | | | | |
| Medical History/Disease History/Demographics | | X | X | | | | | | |
| Physical Exam including Height and Weight | | X | | | | | | | |
| Vital Signs ^a | | X | X | X | X | X | X | X | X |
| Prior/Concomitant Medications ^b | | X | X | X | X | X | X | X | X |
| Adverse Events Assessment ^c | | X | X | X | X | X | X | X | X |
| Study Treatment Administration | | | | | | | | | |
| ASP0598 or placebo ^d | | | X | X ¹ | X ¹ | | | | |
| Otology Examination | | | | | | | | | |
| Microscopic Ear Examination | | X ^e | X ^f | X ^{f,g} | X ^{f,g} | X ^g | X ^g | X ^g | X ⁱ |
| Modified Brighton Grading Scheme Evaluation | | | X ^f | X ^f | X ^f | X | X | X | X |
| Imaging picture of tympanic membrane by endoscope | | X ^e | X ^h | X ^h | X ^h | X | X | X | X |
| Bone conduction by Pure Tone Audiometry (PTA) | | X ^e | X | X ^j | X ^j | X ^j | X ^j | X ^j | X |
| Air conduction by PTA | | X ^e | X | | | | | X | X |
| Tympanometry | | X ^e | X | | | | | X | X |
| Tinnitus Visual Analog Scale (TVAS) | | X | X | X | X | X | X | X | X |
| Blood Collection | | | | | | | | | |
| Serum Chemistries | | X | | | | | | | |
| CBC with Differential | | X | | | | | | | |
| Pregnancy Test ^k | | X | X | | | | X | | X |
| Sample for Future Analysis | | | X | | | | X | | |
| Urine Collection | | | | | | | | | |
| Urinalysis | | X | | | | | | | |

Footnotes appear on next page

AE: adverse event; CBC: complete blood count; EOS: end of study; TM: tympanic membrane; TMP: tympanic membrane perforation

- a. Vital Signs include blood pressure, body temperature, and heart rate.
- b. Includes all medications taken within 28 days prior to ASP0598 Otic Solution or placebo administration at Day 1.
- c. AEs will be collected from the time of informed consent through Day 113 or EOS. Any AEs ongoing at Day 113 or EOS Visit must be followed until resolution or investigator determines the event to be stable. AEs should be assessed at least monthly.

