- d. ASP0598 Otic Solution or placebo will be applied onto the remaining tympanic membrane under a microscope with a 22-gauge blunt needle. After ASP0598 Otic Solution or placebo administration, subjects will be required to remain on their side with the treated ear facing up for at least 15 minutes. Please see the Pharmacy Manual, Section 9.4: Dose Administration for detailed instructions.
- e. Otology examinations will be performed for both ears at the screening visit.
- f. Microscopic Ear examination will be performed prior to and 60 (± 5) minutes after ASP0598 Otic Solution/placebo administration. Skin local reaction at the application site will be evaluated by Modified Brighton Grading Scheme (Appendix 12.9) at 60 (± 5) minutes after ASP0598 Otic Solution/placebo administration.
- g. Ear cleaning will not be conducted between Days 2 – 85, unless it is absolutely necessary. Investigators will not clean the treated ear by suctioning unless subjects experience uncomfortable ear discharge).
- h. At Days 1, 15, and 29, imaging pictures will be taken at the following time points: pre-dose, immediately after, 30 (± 5) minutes, and 60 (± 5) minutes after the ASP0598 Otic Solution or placebo administration.
- i. At Day 85 (SAD) or Day 113 (single dose expansion) and/or EOS, the whole TM should be visible before taking imaging picture. If the whole TM is not visible, the investigator should clean the ear canal.
- j. Bone conduction testing at Day 15, 29, 43, 57, and 85 will be tested only at 1, 2 and 4 kHz (ototoxicity assessment).
- k. Urine or serum pregnancy test will be performed in women of childbearing potential.
- l. ASP0598 Otic Solution or placebo administration on Day 15 and Day 29 will be conducted in the case that the TMP closure is not confirmed.

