6.6 Dose Modification

SAD and single dose expansion

Not Applicable.

MAD

On Day 15 or Day 29, treatment can be skipped at the Investigator's discretion based on safety reasons that interrupt IP administration (e.g., ear canal skin irritation, mild otorrhea). Subjects should be encouraged to return to the office for evaluation and additional IP administration within the Day 15 or Day 29 visit windows. In the case that the investigator is unable to conduct IP administration for anything other than safety reasons, consultation with the sponsor may be required.

Multiple dose expansion

The statement above for MAD is also applicable to the multiple dose expansion. Additionally, the treatment on Day 15 or Day 29, treatment will be skipped in cases where complete closure is confirmed. If the perforation is detected on Day 29 after treatment was skipped on Day 15, IP administration can be conducted.

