On Day 1, Week 2 (multiple dose only), and Week 4 (multiple dose only), 1 h after the treatment, the following ear canal reactions of treated ear will be collected.

Did the ear experience an abnormal ear sensation

- No

- Yes
 - Burning
 - Stinging
 - Itching
 - Pain
 - Other

After Day 1, data for the following parameters will be collected:

- Gel visible in the treated ear (Yes, No)
- Gel visible in the middle ear (Yes, No)
- TMP of treated ear completely closed (Yes, No, Unknown)
- Ear pain (otalgia) in the treated ear (Yes, No)
- Status of the treated tympanic membrane (Normal, Abnormal, Abnormal: Myringitis, Abnormal: Hematoma, Abnormal: Other, Not visible)
- Status of the middle ear in the treated ear (Normal, Abnormal, Abnormal: Mucosal inflammation with effusion, Abnormal: Mucosal inflammation without effusion, Abnormal: Other, Not visible)

Local skin reaction around the application site will be examined at 60 minutes after the treatment at Day 1 and throughout the observation period. Skin toxicity will be evaluated by Modified Brighton Grading Scheme as shown below.

Grade	Description
0	no abnormalities
1	canal erythema
1b	canal erythema with otorrhea (ear canal fluid discharge)
2	canal erythema + swelling, TM still visible
2b	canal erythema + swelling, TM still visible with otorrhea
3	canal erythema + swelling, TM not visible
3b	canal erythema + swelling, TM not visible with otorrhea
4	canal erythema + swelling, TM not visible + erythema and swelling of the pinna
4b	canal erythema + swelling, TM not visible + erythema and swelling of the pinna with otorrhea

Pharmacokinetics:

- Serum concentration of ASP0598 (dose escalation part only)

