6.5.4 Microscopic Ear Examination

On Day 1, Week 2 (multiple dose only) and Week 4 (multiple dose only), 1 hour after the treatment, number and percentage of subjects will be used to summarize the following canal reactions of treated ear by treatment group:

- Did the Ear experience an abnormal ear sensation
 - No
 - Yes
 - Burning
 - Stinging
 - Itching
 - Pain
 - Other

Percentages for the subcategories of 'Yes' will be based on number of subjects with abnormal ear sensation=Yes.

- After Day 1, for categorical endpoints status of the middle ear and status of the treated tympanic membrane, number and percentage of subjects will be used to summarize baseline value and post-baseline value at each specified post-baseline analysis visit by treatment group. Other parameters will be listed only.

Status of the treated tympanic membrane (Normal, Abnormal, Abnormal: Myringitis, Abnormal: Hematoma, Abnormal: Other, Not visible)

Status of the middle ear in the treated ear (Normal, Abnormal, Abnormal: Mucosal inflammation with effusion, Abnormal: Mucosal inflammation without effusion, Abnormal: Other, Not visible)

Percentages for the subcategories of 'Abnormal' will be based on number of subjects with abnormal.

Analysis visits:

SAD	Day 2, Day 3*, Week 1, Week 2, Week 4, Week 8 and EOS
Single dose expansion	Week 2, Week 4, Week 8, Week 12 and EOS
MAD	Week 1, Week 2, Week 3, Week 4, Week 5, Week 8, Week 12 and EOS
Multiple dose expansion	Week 2, Week 4, Week 6, Week 8, Week 12, Week 16 and EOS

*Day 3 evaluations will only be performed for cohorts 1, 2 and 3.

Number and percentage of subjects will be used to summarize the local skin reaction at the application site by grade as assessed by Modified Brighton Grading Scheme.

- Day 1 post dose through end of study visit by grade, grade 1 or above, grade 3 or above
- Day 1 post dose by grade, grade 1 or above, grade 3 or above
- Day 2 by grade, grade 1 or above, grade 3 or above (SAD only)
- Day 3 by grade, grade 1 or above, grade 3 or above (SAD cohorts 1, 2 and 3 only)
- 2nd dose: post dose through end of study by grade, grade 1 or above, grade 3 or above (MAD and multiple dose expansion)
- 2nd dose: post dose on the dosing day by grade, grade 1 or above, grade 3 or above (MAD and multiple dose expansion)

- 3rd dose: post dose through end of study by grade, grade 1 or above, grade 3 or above (MAD and multiple dose expansion)

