- 3rd dose: post dose on the dosing day by grade, grade 1 or above, grade 3 or above (MAD and multiple dose expansion)
- Days 2 to 18 by grade, grade 1 or above, grade 3 or above
- \geq Days 19 by grade, grade 1 or above, grade 3 or above

When assessing severity, if the event changes in severity (0, 1, 1b, 2, 2b, 3, 3b, 4 and 4b where Grade 4b is the worst grade) during a time interval for a subject, the event with the worst grade will be chosen. If the event is reported multiple times with missing grade(s) and with non-missing grade(s) during an analysis period for a subject, then the subject will be counted for the non-missing worst grade. If the event is reported multiple times with all missing grade(s) for a subject, then the subject will be counted as a missing grade.

Refer to Section [6.9.1](#) for end day of end of study visit definition.

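### No pre-dose Modified Brighton grade is scheduled in any part, and the documents disagree on grading when a multiple dose expansion dose is not given

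*Protocol*

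**What the plan says.** **Timing on dosing days.** Footnote f of Table 5 (multiple dose expansion) has the ear examined twice: "Microscopic Ear examination will be performed prior to and 60 (± 5) minutes after ASP0598 Otic Solution/placebo administration". The grade is attached to the second examination only: "Skin local reaction at the application site will be evaluated by Modified Brighton Grading Scheme (Appendix 12.9) at 60 (± 5) minutes after" administration. Tables 2, 3 and 4, and the contingency Tables 13 to 16, carry the same instruction. In the row "Modified Brighton Grading Scheme Evaluation" the Screening cell is blank.

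**When a dose is not given (multiple dose expansion).** Figure 7 footnote h deals with Days 15 and 29: "If the treatment is not conducted on these visits, imaging pictures and Microscopic ear examination for skin local reaction after the drug administration" are to be skipped. Protocol 6.6 withholds the dose when closure is confirmed. It also lets the investigator skip a dose "based on safety reasons that interrupt IP administration (e.g., ear canal skin irritation, mild otorrhea"), a rule written for MAD and extended to multiple dose expansion. Against this, Figure 7 footnote e calls for the grade at every visit, and protocol 7.2.5 calls for skin examination through the whole observation period.

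**Analysis.** The Brighton summaries in SAP 6.5.4 begin after the Day 1 dose and include a row "Days 2 to 18 by grade, grade 1 or above, grade 3 or above". SAP 6.1 bases percentages on subjects with non-missing data.

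**Membrane and middle ear status.** SAP 6.5.4 plans a summary that starts from baseline: "status of the middle ear and status of the treated tympanic membrane, number and percentage of subjects will be used to summarize baseline value". SAP 5.4 introduces the same fields with "After Day 1, data for the following parameters will be collected".

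**The concern.** The Modified Brighton grade is the trial's scale for local skin reaction, and protocol 4.1.1.2 lists it among the blinded data that the Dose Escalation Committee reviews. A grade that exists only after dosing gives no subject-level reference. Erythema already present on Day 1 appears in the tables as a Day 1 post-dose finding. On Days 15 and 29 the only grade comes an hour after the new dose, so anything left from the previous dose is tabulated in the SAP's 2nd-dose or 3rd-dose rows.

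The skipped-dose wording raises a different problem. Doses are withheld both for benefit (closure) and for possible harm (irritation, otorrhea). If grading stops when dosing stops, grades are missing for reasons related to treatment and to the outcome being graded, and probably unequally between arms.

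**Working it through.** The documents give no figure to reproduce. The check sets the passages side by side.

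1. **Baseline grade.** Screening: not scheduled (Tables 2 to 5). Day 1 before dosing: microscopy yes, grade no (footnote f). Day 1 at 60 minutes: grade. SAP 6.5.4: first Brighton row is Day 1 post-dose. No part therefore has a scheduled Day 1 baseline grade. Planned numbers: 20 (SAD) + 16 (MAD) + up to 39 + up to 39 (expansions) = up to 114 subjects. Footnote e, read literally, covers Screening too, but it conflicts with the blank cell and names no pre-dose time.

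2. **Carry-over between doses.** Doses fall on Days 1, 15 and 29.
   - Multiple dose expansion grades on Days 1, 15, 29, 43, 57, 85 and 113, seven visits. None lies between Days 1 and 15 or between Days 15 and 29. The last grade before dose 2 is the one taken 60 minutes after dose 1, two weeks earlier.
   - MAD also has Days 8 and 22, one grade between each pair of doses.
   - SAD and single dose expansion give one dose, so the question does not arise.

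3. **Visit with no dose (multiple dose expansion).** Footnote f supplies only a post-dose grading time, and footnote h removes the post-dose skin examination. Together they leave no scheduled grade. Footnote e and 7.2.5 require one, and Table 5 marks Days 15 and 29 with no stated exception in the Brighton row. Footnote h removes only the examination after administration, so grading at the visit's other microscopic examination is not forbidden. The text does not settle the matter.

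4. **Effect on the SAP if footnote h is followed.** Day 15 is the only multiple dose expansion visit with a target day in Days 2 to 18. An ear with no Day 15 grade has no scheduled grade in that interval and, under SAP 6.1, leaves the denominator. Each ear is 1/13 = 7.7% of a planned group of 13. The number is unknown because no Day 15 closure or skip rate is given; the possible range is 0 to 13 per group. The rows for Day 1 post-dose through end of study and for Day 19 onward still contain these subjects, through the Day 1 grade and the Days 43 to 113 grades.

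5. **Membrane and middle ear status.** Baseline called for: SAP 6.5.4 text, and SAP Table 4, which defines a Baseline window (study day 1 or earlier) for microscopic ear examination. Baseline not provided for: SAP 5.4, which describes collection after Day 1, and the SAP 6.5.4 visit list, which starts at Day 2, Week 1 or Week 2 depending on the part.

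**The case against.** The other side has a good deal to say, and most of it limits the point.

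- Every part has randomised placebo and blinded investigators. Protocol 5.2 excludes canal inflammation that is active or within 3 months before Screening, and likewise active or treated otorrhea. A reader might infer that the grade cannot separate existing from drug-related reaction at all. That goes too far: placebo does this at group level. It does not do it for the individual ear, and a SAD cohort has one placebo subject against four active.
- A reader might infer that skipped ears receive no grade, or that irritation goes unrecorded. The first is one reading of conflicting text. The second is not supported: adverse events are assessed at every visit, otitis externa is an event of special interest, and 6.6 encourages return within the window for evaluation and dosing, which would bring a 60-minute grade.
- Safety analysis is descriptive, the grade is not a primary endpoint, and the escalation stopping rules rest on related adverse events. The skipped-dose issue concerns an expansion part, not escalation. All of this stands.
- A pre-dose grade need not capture erythema from endoscopy, because imaging continues up to 60 minutes post-dose. That stands too; placebo covers it.
- SAP 5.4 does not say the status fields are collected only after Day 1, and the eCRF is not available to check. The finding is therefore an inconsistency within the SAP, not proof that the data are absent.

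**Conclusion.** The point holds in limited form. No Day 1 or same-day pre-dose Brighton grade is scheduled in any part, although the ear is under the microscope at that moment. In multiple dose expansion, persistence from an earlier dose cannot be separated from a new reaction; in MAD this is much weaker. These conclusions rest only on the schedules and footnotes.

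The skipped-dose issue is a contradiction to be reconciled. Under the footnote h reading, two kinds of ear would leave the Days 2 to 18 row: those not dosed on Day 15 because of closure, and those held back for irritation that do not return within the window. Removing irritated ears would make that row look better than it should. The effect of removing closed ears cannot be predicted from the documents. It is tempting to size this from the sample-size closure rates, 13 × 0.80 = 10.4 active and 13 × 0.10 = 1.3 placebo ears. Those rates are planning assumptions for closure at Week 12 or 16, so they do not give a Day 15 count.

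The missing baseline for membrane and middle ear status is a separate inconsistency inside the SAP: as written, the baseline summary is promised without a described source. None of this touches a hypothesis test. It affects how clearly local tolerability can be read.

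**What to change.** - **Protocol Tables 2 to 5 and 13 to 16, footnote f:** record the Brighton grade at the existing pre-dose microscopic examination as well as at 60 minutes.
- **Protocol Figure 7 footnotes e and h, footnote f and 7.2.5:** reconcile them so that a grade is recorded at the Day 15 and Day 29 examination whether or not a dose is given. This concerns the assessment only; the rules for giving or skipping a dose are untouched.
- **Day 1 pre-dose examination:** record tympanic membrane and middle ear status. Align SAP 5.4 and add Baseline to the SAP 6.5.4 visit list.
- **SAP 6.5.4, Brighton summaries:** add a baseline row and change from the Day 1 pre-dose grade. In Days 2 to 18, include the pre-dose and no-dose-visit grades alongside the other grades in the interval, and keep the worst-grade rule. Using the pre-dose grade alone would discard MAD's Day 8 grade and override that rule.

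The cost is a few eCRF fields at examinations already performed, plus footnote and SAP wording. No visit, procedure or assessor is added.

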- f. At Day 57 (SAD) or Day 85 (single dose expansion) and/or EOS, the whole TM should be visible before taking imaging picture. If the whole TM is not visible, the investigator should clean the ear canal.

Figure 7 Otology Examination and PK Blood Draw Flow Chart – Multiple Dose

Days 1, 15, and 29 – Dosing

Through Day 57 except for Days 15 and 29 (MAD) or Through – Day 85 (Multiple Dose Expansion)

Microscopic ear examination^{e, f} / Imaging picture
PTA (Bone at 1, 2, 4 kHz), TVAS

Day 85 (MAD) and Day 113 (Multiple Dose Expansion) or EOS

Microscopic ear examination ^{e, g} / Imaging picture
PTA (Bone + Air), Tympanometry, TVAS

Footnotes appear on next page

EOS: end of study; MAD: multiple ascending dose; PK: pharmacokinetic; PTA: Pure Tone Audiometry; TM: tympanic membrane; TVAS: Tinnitus Visual Analog Scale.

- a. Days 15 and 29, PTA will be conducted only for bone conduction hearing at 1, 2, 4 kHz and Tympanometry will not be conducted.
- b. After ASP0598 Otic Solution or placebo administration, subjects will be required to remain on their side with the treated ear facing up for at least 15 minutes. Please see the Pharmacy Manual, Section 9.4: Dose Administration for detailed instructions.
- c. Days 1, 15, and 29, imaging picture will be taken pre-dose, immediately after, 30 (± 5) minutes and 60 (± 5) minutes after ASP0598 Otic Solution or placebo administration into the affected ear.
- d. Day 1 and Day 29, PK blood draw will be performed pre-dose (-15) minutes, 30 (± 5) minutes and 60 (± 5) minutes after ASP0598 Otic Solution or placebo administration into the affected ear. PK sampling will be performed only during MAD.
- e. Skin local reaction at the ASP0598 Otic Solution/placebo application site will be evaluated by Modified Brighton Grading Scheme (Appendix [12.9](#)) at all visits.
- f. Ear cleaning will not be conducted between Days 2 – 57 (MAD) or Days 2 – 85 for (multiple dose expansion), unless it is absolutely necessary. Investigators will not clean the treated ear by suctioning unless subjects experience uncomfortable ear discharge).
- g. At Day 85 (MAD) or Day 113 (multiple dose expansion) and/or EOS, the whole TM should be visible before taking imaging picture. If the whole TM is not visible, the investigator should clean the ear canal.

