7.1.3 Pure Tone Audiometry

Pure Tone Audiometry (PTA) is a behavioral test and generally the first quantitative hearing test done to assess the nature and degree of hearing loss in adults and in children. This

measure involves the peripheral and central auditory systems. Pure tone air conduction and bone conduction tests determine whether or not there is any hearing loss; what type of hearing loss it is (conductive, sensorineural or mixed hearing loss); the frequencies that are affected (configuration); magnitude of hearing loss (intensity) and whether hearing loss is unilateral or bilateral. The result is plotted on an audiogram, which is a graph displaying intensity as a function of frequency.

PTA will be performed on the bilateral ears at Screening and will be tested only for the treated ear after the treatment side is determined by investigator at Day 1. This will be performed on a calibrated audiometer by a licensed audiologist.

For the efficacy evaluation, PTA will be measured following different frequencies:

Air: 250 Hz, 500 Hz, 1 kHz, 2 kHz, 4 kHz, and 8 kHz

Bone: 500 Hz, 1 kHz, 2 kHz, and 4 kHz

Follow the Schedule of Assessments ([Table 2](#), [Table 3](#), [Table 4](#) and [Table 5](#)) for timing of procedures.

PTA result(s) (decibel at each frequency) will be recorded in the eCRF at each visit.

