Using the non-missing size of TMP per pars tensa surface area, an observed response is

Yes: if the post baseline size of the TMP per pars tensa surface area $\leq 1\%$ and the size of the TMP per pars tensa surface area is smaller than baseline,

No: if the above condition is false.

Ratio of TMP size per total area of tympanic membrane will be used in the above calculation as an approximation for TMP per pars tensa surface area.

- Change from baseline in Air bone (A-B) gap by PTA

For the change from baseline in A-B gap, a negative value (decrease from baseline) indicates an improvement.

PTA is a behavioral test and generally the 1st quantitative hearing test done to assess the nature and degree of hearing loss in adults and in children.

PTA air conduction and bone conduction tests analyzed together determines any hearing loss: type and magnitude of hearing loss; frequencies that are affected; and whether hearing loss is unilateral or bilateral. For both air and bone conduction, a lower value indicates better hearing threshold.

Type of hearing loss can be as follows:

- Conductive hearing loss: when air conduction thresholds are elevated relative to bone conduction thresholds, an “A-B gap” exists, indicates a conductive hearing loss.
- Sensorineural hearing loss: when air conduction and bone conduction thresholds showing the same amount of hearing loss, indicates sensorineural hearing loss.
- Mixed hearing loss: when both air and bone conduction thresholds are elevated, but air conduction thresholds are more elevated than bone conduction thresholds, indicates mixed hearing loss.

Definitions for mean bone conduction hearing, mean air conduction hearing, mean A-B gap and A-B gap (dB) for each frequency are provided below:

Mean bone conduction hearing (dB):

Arithmetic mean of the bone conduction hearing values at 500 Hz, 1, 2 and 4 kHz. If the value is missing for any of the 4 frequencies, then the mean value will be set to missing.

Mean air conduction hearing (dB):

Arithmetic mean of the air conduction hearing values at 500 Hz, 1, 2 and 4 kHz. If the value is missing for any of the 4 frequencies, then the mean value will be set to missing.

Mean A-B gap (dB):

Mean air conduction hearing - mean bone conduction hearing. If either one is missing or both are missing then the mean A-B gap is set to missing.

A-B gap (dB) for each frequency:

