TMP size	Dose expansion: Least squares mean +/- SE for the change from baseline vs Analysis Visit by treatment group (overlay) ^a	Single dose expansion: Baseline, Week 2, Week 4, Week 8, Week 12 and EOS MAD: Baseline, Week 1, Week 2, Week 3, Week 4, Week 5, Week 8, Week 12 and EOS Multiple dose expansion: Baseline, Week 2, Week 4, Week 6, Week 8, Week 12, Week 16 and EOS EOS visit will not be included in the plot.
Time to closure of TMP ^c	Not Applicable	Not Applicable
Air conduction hearing at 250 Hz, 500 Hz, 1 kHz, 2 kHz, 4 kHz and 8 kHz		
Mean air conduction hearing	SAD, MAD and Dose expansion: Individual subject plot of air conduction hearing and bone conduction hearing for each frequency and mean by Analysis Visit (Overlay)	SAD: Baseline, Week 8 and EOS Single dose expansion and MAD: Baseline, Week 12 and EOS Multiple dose expansion: Baseline, Week 12, Week 16 and EOS
Bone conduction hearing at 500 Hz, 1 kHz, 2 kHz and 4 kHz		
Mean bone conduction hearing		
A-B gap at 500 Hz, 1 kHz, 2 kHz, and 4 kHz		
Mean A-B gap		
ECV by tympanometry	Not Applicable	

^a from the MMRM model as described in Section 6.4.2 and Section 6.4.3.

^b Day 3 evaluations will only be performed for cohorts 1, 2, and 3

^c change from baseline is not applicable.

For the secondary endpoint complete closure of TMP at Week 12 (single dose expansion) and Week 16 (multiple dose expansion), number and percentage of subjects will be provided by treatment group for the following subgroups:

- Sex,
- Race,
- Age group,
- BMI group,
- CTMP duration group (≤ 1 year, > 1 to ≤ 10 years, > 10 years),
- Tobacco history (Yes, No),
- Causation of TMP,
- Diabetes history
- Stratification factor TMP size group,
- Baseline TMP size group per total area of tympanic membrane from central imaging.

For the dose expansion secondary endpoints (change from baseline in ratio of TMP size per total area of tympanic membrane and change from baseline in TMP size), descriptive statistics will be used to summarize the Week 12 (single dose expansion) and Week 16 (multiple dose expansion) analysis visit results by treatment group for the subgroup baseline TMP size group per total area of tympanic membrane from central imaging.

For the categories of the subgroup variables, refer to Section [6.2.3](#).

Table 3 Overview of Efficacy Analysis for Dose Expansion

Endpoint Type	Analysis Variable	Analysis Method

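### In multiple dose expansion, the planned Week 12 mean A-B gap and every other Week 12 value that needs 500 Hz bone conduction cannot be derived from the scheduled Day 85 visit

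*Protocol*

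**What the plan says.** **Schedule.** Protocol Table 5 (Section 1.3) schedules air conduction in multiple dose expansion at screening, Day 1, Day 85 and Day 113. Bone conduction is scheduled at every visit, but footnote j restricts it: "Bone conduction testing at Day 15, 29, 43, 57, and 85 will be tested only at 1, 2 and 4 kHz". Table 16, the alternate schedule in Section 12.11, repeats that footnote. Figure 7 (Section 1.2) also shows "PTA (Bone at 1, 2, 4 kHz), TVAS" for the visits through Day 85.

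**Efficacy audiometry.** Protocol Section 7.1.3 lists the efficacy frequencies as "Bone: 500 Hz, 1 kHz, 2 kHz, and 4 kHz", and refers to the schedule for timing.

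**Planned outputs.** SAP Table 2 (Section 6.4) lists bone conduction at 500 Hz, 1, 2 and 4 kHz, mean bone conduction, the A-B gap at each of these frequencies and the mean A-B gap. The visits are "Multiple dose expansion: Baseline, Week 12, Week 16 and EOS". SAP Table 7 gives this part a Week 12 audiometry window of Study Days 72 to 99.

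**Derivation rules.** SAP Section 5.4 defines mean bone conduction as "Arithmetic mean of the bone conduction hearing values at 500 Hz, 1, 2 and 4 kHz" and adds "If the value is missing for any of the 4 frequencies, then the mean value will be set to missing". For the mean A-B gap, the difference between the air and bone means, it says "If either one is missing or both are missing then the mean A-B gap is set to missing".

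**The concern.** The SAP plans a Week 12 summary that the protocol's own schedule leaves empty. Both pathways are tested at Day 85, yet the bone test omits one of the four frequencies that the derivation requires.

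This looks like an oversight. In the four main schedules (Tables 2 to 5), every other post-screening visit with air conduction has unrestricted bone conduction: Day 1 throughout, Day 57 in SAD, Day 85 in single dose expansion and in MAD, and Day 113 in multiple dose expansion.

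Three things are at stake:

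- The Week 12 mean A-B gap is derivable in MAD and single dose expansion but not here, so the time-matched description is lost.
- The EOS value is the last non-missing post-baseline value. A subject whose last audiogram is at Day 85 has an EOS mean air conduction but no EOS mean A-B gap, so the two denominators can differ.
- The SAP uses the same name for a 3-frequency safety mean (Section 5.1) and a 4-frequency efficacy mean (Section 5.4). With 500 Hz absent, a programmer could subtract a 3-frequency bone mean from a 4-frequency air mean, or compare it with a 4-frequency baseline.

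**Working it through.** The documents give no figure to reproduce. The check applies the SAP rules to the frequencies scheduled at each visit.

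**Inputs.** Air conduction at Days 1, 85 and 113 covers 250 Hz, 500 Hz, 1, 2, 4 and 8 kHz (Protocol Section 7.1.3, Table 5). Bone conduction covers 500 Hz, 1, 2 and 4 kHz at Days 1 and 113, and 1, 2 and 4 kHz at Day 85 (footnote j).

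| Variable | Bone frequencies needed | Day 1 | Day 85 | Day 113 |
|---|---|---|---|---|
| Mean air conduction | none | yes | yes | yes |
| Bone conduction at 500 Hz | 500 Hz | yes | **no** | yes |
| 4-frequency mean bone conduction | 500 Hz, 1, 2, 4 kHz | yes | **no** | yes |
| A-B gap at 500 Hz | 500 Hz | yes | **no** | yes |
| A-B gap at 1, 2 and 4 kHz | the same frequency | yes | yes | yes |
| Mean A-B gap | 500 Hz, 1, 2, 4 kHz | yes | **no** | yes |
| 3-frequency safety bone mean | 1, 2, 4 kHz | yes | yes | yes |

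Four planned items fail at Day 85, all through the missing 500 Hz value.

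**Exception at Week 12.** Early terminators complete EOS assessments at discontinuation (Protocol Section 4.1), and footnote j does not restrict the EOS column. A full EOS audiogram on Days 72 to 99 would supply a Week 12 value. Assume drop-out is uniform over Days 2 to 113 (112 days); the window covers 28 of them. Expected number = N × drop-out × 28/112:

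- 26 subjects, 10% drop-out: 26 × 0.10 × 0.25 = 0.65
- 39 subjects, 10% drop-out: 39 × 0.10 × 0.25 = 0.98
- 5% to 20% drop-out: 0.33 to 1.30 of 26, and 0.49 to 1.95 of 39

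So about 0 to 2 subjects in the whole part.

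**Loss at EOS.** Full Day 85 testing could rescue an EOS mean A-B gap only for a subject who attends Day 85 and then leaves. Days 86 to 113 are also 28 of 112 days. Per arm of 13 at 10% drop-out: 13 × 0.10 × 28/112 = 0.325. At 5% to 20% the range is 0.16 to 0.65. These are upper bounds, because anyone who completes an EOS audiogram on leaving loses nothing.

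**The case against.** The strongest reply is that the restriction is deliberate: it stands in two tables and a figure, and Figure 7 shows no air conduction through Day 85. On this view the slip lies in SAP Table 2, where one visit list appears to serve air conduction, bone conduction and A-B gap together. That table is broken in the available text, so assigning the list to these rows is an inference. The outputs are also exploratory, with no statistical analysis planned for them, in a part that opens only if the DMC decides so.

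Much of this stands. The documents do not show which side is the slip, and the consequence is small. The mismatch remains either way. Table 5 does schedule air conduction at Day 85, SAP Table 7 has a Week 12 audiometry window, and SAP Section 6.4.3 plans a Week 12 shift table of air conduction. Section 7.1.3 does not restore 500 Hz, because it defers to the schedule.

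A reader might infer more than the documents support:

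- **That the whole Week 12 A-B gap is lost.** The SAP derives the gap at each frequency, and three of the four remain.
- **That the primary safety bone mean is affected.** It uses only 1, 2 and 4 kHz.
- **That Day 85 yields no efficacy data.** Imaging, air conduction and tympanometry are all scheduled.
- **That 10% drop-out costs 1 to 2 EOS A-B gaps per arm.** This ignores the EOS assessment at discontinuation, and it counts subjects who leave before Day 85 and could not benefit from testing there.

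**Conclusion.** The point holds in a limited form. For every subject tested at the scheduled Day 85 visit of multiple dose expansion, four planned Week 12 items cannot be derived: mean A-B gap, 4-frequency mean bone conduction, 500 Hz bone conduction and 500 Hz A-B gap. Up to 26 or 39 subjects are concerned, depending on the number of groups. An early terminator with a full EOS audiogram in the window is the only exception.

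The EOS loss is at most about 0.3 subjects per arm. The secondary closure and perforation-size endpoints and the Week 16 A-B gap regression do not depend on this visit's bone conduction.

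The conclusion assumes that SAP Table 2's visit list covers the bone and A-B gap rows, and that sites test only the scheduled frequencies. The counts also assume uniform drop-out at the protocol's 10%.

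**What to change.** **Preferred.** Remove Day 85 from the restricted list in footnote j of Protocol Tables 5 and 16, so that 500 Hz bone conduction is tested there. Align Figure 7, which otherwise would still limit bone conduction through Day 85 and show no air conduction. The cost is one extra frequency in an audiometry session already scheduled, plus edits to two footnotes and a figure. All four items then become derivable at Week 12 for every subject who attends.

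**Alternative, if the sponsor keeps the restriction.** Remove from the Week 12 multiple dose expansion entries of SAP Table 2 only the 4-frequency mean bone conduction, mean A-B gap, 500 Hz bone conduction and 500 Hz A-B gap. Keep the 1, 2 and 4 kHz values, which are valid. This needs only a SAP edit, but gives up the Week 12 mean A-B gap in this part.
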